### 7.1.3 Supportive and Sensitivity Analyses

To assess the robustness of the study results, supportive analyses of OS will be performed using modified ITT and per protocol population. In addition, the following sensitivity OS analyses will be performed, if appropriate:

Patients will be censored at the time when they received other non-protocol required anticancer treatment, if applicable.

Patients will be censored at the time when they drop out of the study due to AEs.

Exploratory analyses of the effect of baseline characteristics and other covariates will be conducted using Cox regression models. Cox models with treatment (forced into the model) and different (see listed underneath) covariates each at the time, and a global Cox model with treatment (forced into the model) and different covariates using backward selection will be made. The significance level to retain a variable in the model will be set at 10%. The following covariates will be considered:

- Age (entered as continuous covariate)
- Endometrial cancer type: Type I vs Type II  
Type I: endometrioid, squamous, adenocarcinoma (recorded under ‘other’)  
Type II: serous, clear cell, mixed, carcinosarcoma (recorded under ‘other’)  
(additional histology variants captured under ‘other’, will be assigned to Type I or II as medically appropriate)
- Histology: endometrioid vs serous vs clear cell vs squamous cell carcinoma vs other
- Tumor grade: Gx vs G1 vs G2 vs G3 vs G4 vs other
- Prior radiotherapy (yes vs no)
- Time since diagnosis (< 12 months vs  $\geq$  12 months)
- Stage of disease at study entry (advanced or recurrent disease vs metastatic disease)
- Potential center-effects  
Territory (North America vs W/N-Europe vs Eastern Europe)
  - North America: US, CA
  - W/N-Europe/Israel: AT, BE, DE, DK, ES, FI, GB, IE, IL, IT, NL, NO, PL
  - Eastern Europe: BG, BA, BY, CZ, RU, UA, RORecruitment volume (‘low recruiters’ vs ‘high recruiters’)
  - low recruiter: < 10 patients/site
  - high recruiter:  $\geq$ 10 patients/site

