8.6.2 Follow-up for survival

For patients going off study, survival information will be collected at 3-month intervals, telephone contact is acceptable.

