9.4.3 Sensitivity analyses

The following sensitivity OS analyses will be performed:

1. Patients who changed treatment will be censored at the day the patient received the new treatment;
2. PP analysis.

Additional sensitivity analyses may be performed as appropriate.

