#### 7.1.1 OS: Definition

OS is defined as the time from randomization to death for any cause during the study. Patients without confirmed vital status are censored on the day they are last known alive. Every reasonable effort will be made to establish vital status of each patient on the last day of the study, that is, the clinical cutoff date established after approximately 384 patients have died. OS will be calculated as follows:

For those who die during the study,

$$\text{overall survival (days)} = \text{date of death} - \text{randomization date} + 1;$$

For those who are alive or vital status cannot be determined at the end of the study,

$$\text{overall survival (days)} = \text{date of censoring} - \text{randomization date} + 1, \text{ with censor indicator indicating a censor.}$$

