#### 7.1.2 OS: Primary Analysis

The primary analysis of OS will be performed using the ITT population.

The primary efficacy analysis will be performed using the ITT population. The final analysis, which is event-based, will be conducted after approximately 384 randomized patients have died. In the primary analysis, a log-rank test with an overall two-sided Type I error rate of 0.05 after taking the interim analyses into account will be used to compare OS between the two treatment arms via a SAS lifetest procedure. Kaplan-Meier estimates will be used to calculate median OS and the 95 % confidence interval of the median OS. The proportion of patients alive at six and 12 months (from randomization date) and the 95 % confidence intervals for these estimated proportions, if appropriate, will be presented.

A Cox model with treatment effects will be used to estimate the hazard ratio and perform hypothesis testing. The estimated hazard ratio and the 95 % confidence interval of the hazard ratio will be presented.

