## 12.5 Appendix E – List of Tables/Graphs and Listings

### List of Statistical Tables

Number	Description CODE: GREEN = topline; needed first
Table 14.1.1.1	Patient disposition
Table 14.1.1.2	Patient disposition by investigational site
Table 14.1.1.3	Patient disposition by territory
Table 14.1.2	Major protocol deviations
Table 14.1.3.1	Patients demographics and baseline characteristics (ITT)
Table 14.1.3.2	Patients demographics and baseline characteristics (safety)
Table 14.1.4.1	History of endometrial cancer (ITT)
Table 14.1.4.2	History of endometrial cancer (safety)
Table 14.1.5	Prior treatment for endometrial cancer
Table 14.1.6.1	Prior medications
Table 14.1.6.2	Concomitant medications
Table 14.1.7.1	Treatment exposure (ITT)
Table 14.1.7.2	Treatment exposure (safety)
Table 14.1.7.3	Treatment – mode of administration (ITT)
Table 14.1.8.1	Treatment modifications (ITT)
Table 14.1.8.2	Treatment modifications (safety)
Table 14.1.9	Post-study treatment anticancer therapy
Table 14.2.1	Overall survival: primary analysis (ITT)
Table 14.2.2	Overall survival: sensitivity analysis 1 (PP)
Table 14.2.3	Overall survival: sensitivity analysis 2 (MITT)

Table 14.2.4	Overall survival: sensitivity analysis 3 (ITT, censoring at time subject drops out due to AE)
Table 14.2.5.1	Overall survival: sensitivity analysis 4: part 1 (Cox models for treatment and each covariate separately)
Table 14.2.5.1	Overall survival: sensitivity analysis 4: part 2 (multivariate Cox model)
Table 14.2.6	Overall response rate: primary analysis
Table 14.2.7	Overall response rate: sensitivity analysis 1 (PP)
Table 14.2.8	Overall response rate: sensitivity analysis 2 (MITT)
Table 14.2.9.1	Overall response rate: sensitivity analysis 3: part 1 (logistic regression models for treatment and each covariate separately)
Table 14.2.9.2	Overall response rate: sensitivity analysis 3: part 2 (multivariate logistic regression model)
Table 14.2.10	Duration of overall response
Table 14.2.11	Duration of stable disease
Table 14.2.12	Duration of follow-up
Table 14.2.13	Progression-free survival: primary analysis
Table 14.2.14	Progression-free survival: sensitivity analysis 1 (PP)
Table 14.2.15	Progression-free survival: sensitivity analysis 2 (MITT)
Table 14.2.16	Progression-free survival: sensitivity analysis 3 (MITT – selection of patients with CR, PR or SD as best overall response)

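### The OS sensitivity analysis that censors at dropout for adverse events discards recorded deaths and cannot support robustness; censoring at new anticancer therapy has a similar, conditional weakness

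*SAP*

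**What the plan says.** SAP 7.1.3 follows the modified ITT and per-protocol analyses with a second group, introduced by "In addition, the following sensitivity OS analyses will be performed, if appropriate". It contains two censoring rules for OS:

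- New therapy: "Patients will be censored at the time when they received other non-protocol required anticancer treatment, if applicable".
- AE dropout: "Patients will be censored at the time when they drop out of the study due to AEs".

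Protocol 9.4.3 has a counterpart to the first rule, "Patients who changed treatment will be censored at the day the patient received the new treatment", but none to the second. SAP Appendix E schedules an output for the AE rule, "Overall survival: sensitivity analysis 3 (ITT, censoring at time subject drops out due to AE", as Table 14.2.4 with a matching Kaplan-Meier figure. It lists no output for new-therapy censoring.

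The primary analysis is different. "OS is defined as the time from randomization to death for any cause during the study", and "The primary analysis of OS will be performed using the ITT population". Only patients who are alive or of unknown vital status are censored (SAP 7.1.1).

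On follow-up, Protocol 8.6.2 states: "For patients going off study, survival information will be collected at 3-month intervals, telephone contact is acceptable". SAP 2.2 says that all patients are followed for survival. Footnote 3 of the flow chart keeps patients who cannot be retreated because of toxicity under follow-up for outcome.

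**The concern.** Kaplan-Meier and Cox methods assume that a censored patient has the same later risk of death as a comparable patient still under observation. Neither event here is likely to meet that assumption. Withdrawal for poor tolerability or cardiac toxicity (Protocol 5.3) covers LVEF decline, heart failure and myocardial infarction. Later anticancer therapy is chosen by the investigator from disease signs and persisting toxicity (Protocol 6.4), so it usually marks progression. The trial is open-label and the two drugs have different dose-modification rules (Protocol 6.1.3 and 6.2.3), so rates may differ between arms.

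An excess of toxicity-related deaths in one arm would mostly follow AE dropout. The AE rule removes those deaths from the comparison. A censored result that agrees with ITT could then be read as reassurance when it carries none, and one that disagrees could be an artefact.

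**Working it through.** **1. The plan's own figure.** Medians of 12 and 9 months give HR = 9/12 = 0.75 under exponential survival. Schoenfeld: deaths = 4(1.960 + 0.842)² / (ln 0.75)² = 31.4 / 0.0828 ≈ 380. Allowing for the O'Brien-Fleming-type look at 50% information gives 380.8, and 384 deaths give power 0.803. The stated 384 is reproduced. It belongs to the ITT analysis, which neither censoring rule touches.

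**2. What dropout means.** SAP 7.1.3 speaks of leaving the study. The AE listing in SAP 9.1 identifies AE dropout with the CRF entry for drug withdrawn. Protocol 5.3 uses withdrawal for stopping either treatment or follow-up.

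| Reading | Vital status afterwards | Effect of the AE rule |
|---|---|---|
| Study drug stopped (SAP 9.1) | Still collected | Recorded deaths are discarded |
| Follow-up stopped | Usually unknown | SAP 7.1.1 already censors at last known alive, so the primary analysis is largely repeated |

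Neither reading gives a robustness test. The SAP also does not say whether a patient with a fatal AE counts as a death or as a censored dropout.

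**3. AE rule when dropout marks added harm.** The documents give no dropout rates, so the rates, hazard multipliers and timing are assumptions. Simulation: 250 patients per arm, 24 months' accrual, cutoff at the 384th death, median OS 9 months in both arms before dropout, death hazard multiplied by k afterwards, 1,000 trials per row.

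| Dropout, AEZS-108 vs doxorubicin | k | ITT HR | AE-censored HR | Deaths kept |
|---|---|---|---|---|
| 10% vs 10% | 3 | 1.00 | 1.00 | 346 |
| 20% vs 10% | 2 | 1.05 | 1.00 | 332 |
| 20% vs 10% | 3 | 1.07 | 1.00 | 328 |
| 30% vs 10% | 2 | 1.10 | 0.99 | 315 |
| 30% vs 10% | 3 | 1.15 | 1.00 | 310 |

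The reason is structural. Before dropout the hazards are equal, and only that period is analysed, so the censored HR is 1.00 whatever happens later. In the last row ITT detects harm in 28% of trials and the censored analysis in 2.5%, which is the nominal one-sided rate. Large-sample runs at 20-25% versus 10%, with dropout spread over 0.7 to 6.2 months, gave the same picture: ITT HR 1.04-1.09 became 0.99-1.00. With the excess in the other arm, 0.91-0.96 became 1.00.

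**4. AE rule when dropout marks prognosis and true OS is identical.** With a threefold hazard contrast, 20% versus 20% gives HR 0.99, 20% versus 10% gives 0.97, 30% versus 10% gives 0.94 and 40% versus 20% gives 0.93. The bias favours the arm with more dropout.

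**5. New-therapy rule, identical true OS.** Assumed: median time to progression 4 months, death hazard 0.03 per month before and 0.14 after, new therapy within a month of progression.

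| Use among progressors, AEZS-108 vs doxorubicin | Censored HR | False result | Deaths kept |
|---|---|---|---|
| 50% vs 50% | 1.00 | about nominal | 240 |
| 60% vs 40% | 0.90 | favours AEZS-108, 12.7% | 240 |
| 40% vs 60% | 1.10 | favours doxorubicin, 12.2% | 240 |

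The nominal false rate in one direction is 2.5%. At 60% versus 40%, other hazard pairs (after/before progression) give 0.91 (0.11/0.02), 0.95 (0.095/0.04) and 0.97 (0.09/0.05). Equal use protects the HR but not the medians: with 50% in both arms and 0.11/0.02, median OS moved from 10.8 to 12.3 months.

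**6. Scale.** With 384 deaths the standard error of log HR is about 2/√384 = 0.102. The AE-rule shift from 1.10 to 1.00 is ln 1.10 = 0.095. The new-therapy shift to 0.90 is |ln 0.90| = 0.105. Both are about one standard error. Losing deaths also costs precision: at HR 0.75, 300 deaths give 70% power and 250 give 62%.

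**The case against.** No decision rests on these analyses. The primary test is ITT with death from any cause, and the hierarchy in SAP 7.4 runs OS, PFS, ORR. The two rules apply only if judged appropriate, and the SAP's robustness wording opens the preceding sentence, on modified ITT and per-protocol. This stands and limits the point. The rules are nevertheless named sensitivity analyses in the same section, and that invites a robustness reading.

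A reader might infer that the plan hides toxicity deaths. The documents do not support this. Every death stays in Table 14.2.1. Deaths and fatal events also appear in Tables 14.3.1.15 (grade 5 serious TEAEs), 14.3.2.5 and 14.3.2.6 (all deaths, and deaths within 30 days of the last dose) and in Listings 16.2.7.7 and 16.2.7.8. They are lost only within the censored analysis.

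The sizes depend on assumed differences between arms. Nothing in the documents implies a 20-point gap in later therapy. Protocol 1.2.2 reports that in the Phase II endometrial study no AEs other than deaths or SAEs led to stopping AEZS-108. That was a study of 43 patients without a doxorubicin arm, so it does not settle the difference here, but smaller gaps are possible and would give smaller shifts.

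A reader might also conclude that new-therapy censoring must be replaced by inverse-probability-of-censoring weighting. That goes too far. The protocol itself plans the simple analysis, and in post-treatment follow-up ECOG is recorded only until progression, so a key time-varying predictor is missing when new therapy usually starts.

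**Conclusion.** The point holds for the sensitivity analyses only. The AE-dropout rule, read with SAP 9.1 and the survival follow-up provisions, discards recorded deaths in patients likely to be at higher risk. It cannot show whether the ITT result is robust. At 20-25% versus 10% dropout and 2 to 3 times the hazard afterwards, an ITT HR of about 1.05-1.10 is displayed as about 1.00.

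New-therapy censoring has the same weakness conditionally. The HR moves to about 0.90 or 1.08-1.10 when use differs 60% versus 40% and hazard is much higher after progression. It moves less with a smaller hazard step and stays near 1.00 with equal use. A spurious difference in HR therefore needs both a prognostic link and an imbalance between arms. All rates and multipliers are assumptions.

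It would be wrong to infer that the primary OS result is biased. The ITT log-rank test, its alpha and the 384-death target are unaffected.

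**What to change.** - Delete the AE-dropout censoring analysis (Table and Figure 14.2.4). Otherwise label it descriptive and state that no robustness conclusion will be drawn from it.
- Keep every recorded death as an OS event in any analysis offered as evidence of robustness.
- Reconcile dropout from the study in SAP 7.1.3 with drug withdrawn in SAP 9.1. If the analysis is kept, state how a fatal AE is handled.
- Keep new-therapy censoring, in line with Protocol 9.4.3, but label it descriptive. State its independent-censoring assumption, report the number and timing of censored patients by arm, and add the missing output to Appendix E.
- Treat inverse-probability-of-censoring weighting as optional, with its model assumption and the ECOG limitation stated.

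The cost is SAP wording and a small table on data already collected. The downside is that one planned output is lost or carries a caveat.

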### 7.2 Secondary Efficacy Outcomes

The study has two key secondary efficacy outcomes: progression free survival (PFS) and overall response rate (ORR).

### **7.2.1 ORR and Clinical Benefit: Definitions**

The ORR for each treatment arm will be estimated as the proportion of responders, defined as a patient whose best overall response is PR or better during the treatment period. All responses must be confirmed at least 4 weeks after the initial response is seen. Tumor assessments will occur every 3 cycles ( $\pm 7$  days) during ongoing treatment then, if required beyond the end of treatment, every 3 months ( $\pm 7$  days) while the patient is on study. The last assessment will occur either when progression is confirmed or when approximately 384 randomized patients have died.

Clinical benefit is defined as having stable disease or better lasting for at least 9 weeks.

### **7.2.2 ORR and Clinical Benefit: Primary Analysis**

The ITT population will be used to test the effects of AEZS-108 and comparator on ORR.

Hypothesis testing between the two treatment arms will be performed using a Mantel-Haenszel test. The corresponding odds ratio will be also estimated. The 95 % confidence interval of the ORR will be reported via normal approximation without continuity correction.

Clinical benefit rate will be analyzed using the same methods for the ORR analyses.

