The final analysis will be performed after about 384 deaths have been observed. There will be two planned interim analyses; the first will be for futility only, the second will be for safety and efficacy.

Based on the availability of the assay for LHRH receptor expression in tumor specimens, subgroup analyses stratified for extent of LHRH receptor expression will assess the predictive value of the LHRH receptor assay.

A sub-study, at selected sites, will investigate the pharmacokinetics of AEZS-108, doxorubicin and doxorubicinol and assess the acute effects on electrocardiographic parameters.

Sparse PK sampling will be performed, at all sites where feasible, to explore exposure-response relationships between AEZS-108 and its metabolites and measures of safety and efficacy.

Number of patients planned

Approximately 500 (250 per treatment arm).

Inclusion criteria

1. Women \geq 18 years of age
2. Histologically confirmed endometrial adenocarcinoma of any subtype.
 - a. Endometrioid carcinoma
 - i. Variant with squamous differentiations
 - ii. Villoglandular variant
 - iii. Secretory variant
 - iv. Ciliated cell variant
 - b. Mucinous adenocarcinoma
 - c. Serous adenocarcinoma
 - d. Clear cell adenocarcinoma
 - e. Mixed cell adenocarcinoma
 - f. Squamous cell carcinoma
 - g. Transitional cell carcinoma
 - h. Small cell carcinoma
 - i. Undifferentiated carcinoma

3. Advanced (FIGO stage III or IV), recurrent or metastatic disease.
4. Measurable or non-measurable disease that has progressed since last treatment.
5. Patients with advanced, recurrent, or metastatic endometrial cancer who have received one chemotherapeutic regimen with platinum **and** taxane (either as adjuvant or as first line treatment) and who have progressed.
6. Availability of fresh or archival FFPE tumor specimens for analysis of LHRH receptor expression.

Exclusion criteria

Safety concerns:

1. ECOG performance status > 2.
2. Inadequate hematologic, hepatic or renal function
 - thrombocyte count: < 100 x 10⁹/L;
 - absolute neutrophil count (ANC): < 1.5x 10⁹/L;
 - hemoglobin: < 5.6 mmol/L (< 9 g/dL);
 - ASAT, ALAT, AP: > 2.5 times upper limit of normal range (ULN) (> 5x ULN if clearly related to liver metastases);
 - creatinine, bilirubin: > 1.5x ULN.
3. Red blood cell transfusion within 2 weeks prior to anticipated start of study treatment.
4. History of myocardial infarction, acute inflammatory heart disease, unstable angina, or uncontrolled arrhythmia within the past 6 months.

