1 BACKGROUND INFORMATION AND RATIONALE

1.1 Background information on LHRH receptors and endometrial cancer

LHRH receptor expression in gynecological cancers

LHRH, also known as GnRH, is a hormonal decapeptide produced by the hypothalamus, which plays a pivotal role in the regulation of the pituitary/gonadal axis, and thus, in the production of sex steroids. Because sex steroids have been implicated in the development of breast and other gynecological cancers, the role of LHRH and its receptor in these tumors has been studied. While breast cancers were found positive for LHRH receptors in up to 50 % of cases, more than 80 % of ovarian and endometrial cancers have been reported to have functional binding sites for LHRH [17, 21, 22], which are targeted by AEZS-108 (see [Section 1.2.1](#) below).

Endometrial cancer

Cancer of the endometrium is the most common gynecologic malignancy and accounts for 6 % of all cancers in women. The majority of the cases occur in postmenopausal women, with the largest number of women developing their cancers during the sixth decade.

The most common histological form of endometrial cancer cell type (about 80 % of all cancers) is endometrioid adenocarcinoma [18]. Serous, clear cell, mucinous, squamous, and undifferentiated tumors are rarely encountered. While in many cases primary therapy of endometrial cancer results in cure, in some 25 % of the patients recurrences are seen, commonly within 3 years after diagnosis. Recurrent tumors locally confined to the vagina may be cured in some cases with combined surgery and radiation therapy; systemic recurrences are usually considered incurable and are typically treated with systemic therapy.

Systemic drug therapy

Patients with advanced or recurrent tumors that are progesterone receptor-negative or do not respond to hormonal therapy should be considered for chemotherapy.

Active agents include anthracyclines, platinum compounds, and taxanes. Observed single agent response rates vary between 20-35 %. Responses rates have increased when various combination therapies were employed although it remains unclear whether this confers any survival advantage [4, 15, 19].

Please refer to [Section 1.3](#) for details on the selection of doxorubicin as comparator drug for this study.

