1.3 Rationale for the present study

Selection of doxorubicin as comparator drug

In recent years, there has been a trend towards use of carboplatin/taxane for first line chemotherapy, so that doxorubicin whether as non-liposomal or pegylated liposomal doxorubicin (PLD) formulation is increasingly used in second line chemotherapy. Moderate response rates, however, have been reported for PLD when used in patients with prior chemotherapy (9 %) [16], but also in patients without prior chemotherapy (11.5%) [14], which could have been due to the selection of patients with less favorable prognosis for the latter trial [19].

Based on the reported moderate activity of PLD when used for second line therapy of endometrial cancer, non-liposomal doxorubicin has been selected as comparator drug in this trial.

The selection of doxorubicin as comparator drug in this trial implies that prior use of doxorubicin for advanced/recurrent disease is excluded.

Clinical assumptions underlying the statistical planning and sample size estimate

This study is planned to include patients who have relapsed or progressed on or after platinum/taxane-based chemotherapy. Therefore, the statistical plans for the present study are based on the following considerations.

Overall survival of endometrial cancer patients after use of doxorubicin in first line therapy was found at 7 months [1] and 9 months [20]. While shorter survival could be assumed if the drug is used in pretreated patients, better knowledge on the use of rescue treatments and improved patient care could lead to similar overall survival as seen in previous (first line chemotherapy) study. For comparison, median overall survival in a recent Phase II study of ixabepilone in pretreated patients was found at 8.7+ months [5]. Thus, the current study is planned under the assumption of a 9 month overall survival for the control arm.

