### 2.2 Study Design

This is an open-label, randomized, active-controlled, two-arm Phase III study to compare the efficacy and safety of AEZS-108 and doxorubicin. The study will include about 500 patients with advanced, recurrent or metastatic endometrial cancer who have

progressed and who have received one chemotherapeutic (i.e., cytotoxic) regimen with platinum and taxane (either as adjuvant or first line treatment).

Patients will be centrally randomized in a 1:1 ratio to receive treatment with either AEZS-108 (Arm A) or doxorubicin (Arm B).

During ongoing treatment, response will be evaluated every 3 cycles; earlier reassessments should be scheduled to verify a response (at least 4 weeks after first observation of the response) or in case of suspected progression. Patients, who have gone off-treatment for reasons other than progression, will be reassessed every 12 weeks until progression. All patients will be followed-up for survival.

On a regular basis, at intervals no longer than 6 months, results from safety analyses will be submitted to an independent Data and Safety Monitoring Board (DSMB) that will advise the Sponsor of potentially critical findings.

The final analysis will be performed after about 384 deaths have been observed. There will be two planned interim analyses; the first will be for futility only, the second will be for safety and efficacy.

Based on the availability of the assay for LHRH receptor expression in tumor specimens, subgroup analyses stratified for extent of LHRH receptor expression was planned to assess the predictive value of the LHRH receptor assay. Due to non-availability of a validated assay, no such stratified analyses can be performed.

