## 4 GENERAL CONVENTIONS

Unless otherwise stated, all analyses will be performed using SAS Version 9.2 or higher and all hypothesis tests will be conducted at a two-sided significance level of 0.05. P-values will be presented with 3 decimals and p-values that are less than 0.001 will be presented as < 0.001.

Continuous (non-survival related) data will be summarized using descriptive statistics: number of observations (n), mean, standard deviation (SD), median, minimum, and maximum. Frequencies and percentages will be used to summarize categorical (discrete) data. Presentations of categorical data will generally suppress percentages for items where the count is zero in order to draw attention to the nonzero counts. In general, mean, standard deviation, median, 25th and 75th percentiles, minimum, maximum, and percentages will be presented with one decimal.

Unless otherwise stated, confidence intervals, when presented, will be constructed at the two-sided 95 % level. For binomial variables, the 95 % confidence intervals will be constructed using the normal approximation without continuity correction.

In the tables the following indication for treatment will be used: AEZS-108 and Doxorubicin. Data listings will show data presented in the summary tables by study drug, country, center and patient number.

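### The per-arm ORR interval is specified as a plain normal approximation, which under-covers modestly, mainly at the upper limit, if the control response rate is near 9-11.5%; a named score or exact interval avoids this at no cost

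*SAP*

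**What the plan says.** SAP 7.2.2 fixes the interval method for the response rate: "The 95 % confidence interval of the ORR will be reported via normal approximation without continuity correction". SAP section 4 makes this the general rule: "For binomial variables, the 95 % confidence intervals will be constructed using the normal approximation without continuity correction". No score or exact interval is planned anywhere, and the supportive ORR analyses in SAP 7.2.3 do not add one.

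The denominator is all randomized patients: "The ITT population will be used to test the effects of AEZS-108 and comparator on ORR". The planned size in the protocol synopsis is "Approximately 500 (250 per treatment arm").

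The arms are compared by a Mantel-Haenszel test with an odds ratio (SAP 7.2.2); Protocol 9.5.2 adds a confidence interval for the odds ratio. ORR stands third in the hierarchy, after OS and PFS, and is analysed with a view to labelling (SAP 7.4).

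Neither document states an expected ORR for the control arm. Protocol 1.3 cites 9% and 11.5% for pegylated liposomal doxorubicin, in pretreated and chemotherapy-naive patients respectively. Protocol 1.1 says of active agents in general, anthracyclines included: "Observed single agent response rates vary between 20-35" %.

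**The concern.** The Wald interval is centred on the observed proportion and takes its width from the same proportion. When a low rate is observed by chance to be lower still, the estimated standard error shrinks with it, and the upper limit is pulled too far down. Coverage then falls below 95%, and the misses collect on one side.

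Three features of the design make a low ORR plausible. The denominator is ITT. Responses must be confirmed after at least 4 weeks (SAP 7.2.1). Patients with non-measurable disease are admitted (Protocol 5.1), and under Table 2 of Protocol 7.1.5.3 they can reach CR but have no PR category.

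What is at stake is whether the 95% limits printed beside a key secondary endpoint mean what they say. No decision in the trial depends on them.

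**Working it through.** **Inputs.** n = 500 / 2 = 250 per arm (protocol synopsis). Interval method from SAP 4 and 7.2.2, read as Wald. True response rates: 9-11.5% (Protocol 1.3, liposomal drug) and 20-35% (Protocol 1.1). The rates are scenarios, because the plan assumes none.

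**The plan's own figure.** There is no ORR sample size or power to reproduce. The patient number rests on 384 deaths for OS. With HR = 9/12 = 0.75, Freedman's formula gives (1.75/0.25)² × (1.960 + 0.842)² = 49 × 7.849 ≈ 385 deaths, and Schoenfeld's gives 4 × 7.849 / (ln 0.75)² ≈ 380. Both agree with the plan, so 250 per arm is a sound basis.

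**Formulas**, with p̂ = x/n and z = 1.96:
- Wald: p̂ ± z√(p̂(1−p̂)/n)
- Wilson: [p̂ + z²/2n ± z√(p̂(1−p̂)/n + z²/4n²)] / (1 + z²/n)
- Exact coverage at true rate p: the sum of the Binomial(250, p) probabilities over all x whose interval contains p.

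**One point in full, p = 9%.**
- Wald: 15 responders give an upper limit of 6.0% + 1.96 × √(0.06 × 0.94/250) = 8.94%, so every x ≤ 15 misses from below. P(X ≤ 15) = 5.5%. The lower limit exceeds 9% from x = 33; P(X ≥ 33) = 1.7%. Coverage = 100 − 5.5 − 1.7 = 92.8%.
- Wilson: misses occur at x ≤ 13 (1.8%) and x ≥ 32 (2.8%). Coverage = 95.4%.

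**Other rates, Wald, n = 250.**

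| True ORR | Coverage | Upper limit too low (nominal 2.5%) |
|---|---|---|
| 9% | 92.8% | 5.5% |
| 10% | 93.2% | 5.1% |
| 11.5% | 94.1% | 4.6% |
| average over 9-11.5% | 94.2% | 4.4% |
| average over 20-35% | 94.7% | 3.2% |
| average over 50-80% | 94.8% | 2.3% |

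The averages use steps of 0.05 percentage points. Coverage oscillates because the binomial is discrete, so some rates between 9% and 11.5% do reach 95%, and the average is the fairer summary.

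**After the change.** Over 9-11.5% Wilson averages 95.1%, with the upper limit too low 2.0% of the time and the lower limit too high 2.9%. Clopper-Pearson averages 96.1%, with neither tail above 2.5%. Over 20-35% Wilson averages 95.0%.

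**Size on the page.** With 23/250 responders (9.2%): Wald 5.6-12.8%, Wilson 6.2-13.4%, Clopper-Pearson 5.9-13.5%. Moving from Wald to Wilson shifts each limit by about 0.6 points. With 22/250 (8.8%): Wald 5.3-12.3%, Wilson 5.9-13.0%, shifts of about 0.6 and 0.7 points.

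**Effect on the comparison.** A Wald interval for the difference in ORR (which the plan does not call for), with true rates of 9% and 15% and 250 per arm, has its lower limit too high 2.4% of the time and its upper limit too low 2.7%. The tails are close to balanced, because the skew in one arm largely offsets that in the other.

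**The case against.** The strongest objection is to the rates. The 9% and 11.5% belong to a formulation the sponsor chose not to use: Protocol 1.3 gives its moderate activity as the reason for selecting non-liposomal doxorubicin. The protocol also cites 20-35% for active single agents, and there the shortfall is 0.3 points. This stands, and it makes the point conditional. It does not remove it: the plan commits to no control rate, the three design features above all push ORR down, and an interval that is well calibrated in both ranges is available.

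A second objection is that the method is pre-specified and consistent between SAP 4 and 7.2.2, and the limits move by well under one point. Both are true, and they set the weight of the point.

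A third is that the Wilson interval also rests on a normal approximation with no continuity correction. If that was meant, there is no defect; but the text does not say so, and most programmers would produce Wald from it.

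A reader might also infer that a control-arm upper limit set too low flatters AEZS-108. The documents do not support this. The arms are compared by the Mantel-Haenszel test and the odds ratio, and the single-arm interval enters neither. The same interval is used in both arms, and the check on the difference shows nearly balanced tails.

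**Conclusion.** The point holds as a minor reporting matter, conditional on a low control ORR. With 250 patients per arm and a true rate of 9-11.5%, the specified interval covers 94.2% on average instead of 95%, and its upper limit is too low 4.4% of the time instead of 2.5%. The worst of the three tabulated rates is 9%: 92.8% and 5.5%. At 20-35% it is close to nominal. These figures assume that the SAP wording means Wald and that the arms reach their planned size. The arithmetic is firm; the control rate is not.

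The finding should not be extended to the clinical benefit rate because SAP 7.2.2 gives it the same method. Phase II rates were 69.8-76.7% (Protocol 1.2.2), and over 50-80% Wald coverage is 94.8%. Nor should it be extended to complete responses alone, for which SAP 7.2.2 plans no separate analysis. The test, the hierarchy and the sample size are unaffected.

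**What to change.** In SAP 7.2.2, name the Wilson score interval for the ORR in each arm, or Clopper-Pearson if coverage of at least 95% is wanted at the price of slightly wider limits. Amend the binomial sentence in SAP section 4 to match, so that the two places do not conflict. If Wilson was already intended, saying so is enough. No change is needed to the odds ratio, the Mantel-Haenszel test or the clinical benefit analysis. The cost is one phrase in each section and one SAS option, with no new data and no effect on any test.
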